If this approach proves successful, it has the potential to result not only in a large increase *in the number* of organs available in the cardiac donor pool but also an overall increase *in the quality* of organ offers. The reason for this is that, unfortunately, many potential donors who are HCV-positive belong to a young demographic, aged 18 to 35 years, who are now caught up in the national epidemic of opioid and intravenous drug abuse, their deaths resulting from drug overdosing. Sadly, despite availability of curative HCV therapies, very few intravenous drug users (IVDUs) are able to access these therapies. Thus, it is estimated that the HCV epidemic will continue to spread amongst young IVDUs throughout the foreseeable future. HCV-positive donor hearts originating from this potential donor cohort, by virtue of their young age and statistical estimates of projected allograft performance after transplantation, may be

some of the most robust in the cardiac donor pool. Demonstration of successful preemptive and/or immediate post-transplant treatment of HCV in this model could expand the viable cardiac donor pool and result in a reduction in morbidity, mortality, and long-term healthcare costs for patients with end stage heart disease.

***Please note, throughout this protocol the use of HCV-positive refers to HCV nucleic acid testing (NAT)-positive organs. We address evaluation and management of NAT-negative organs under the Study Procedures section of this document and in the separate Protocol Summary document.***

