## **II. Specific Aims**

### ***Primary Objective - Aim 1***

Determine if preemptive administration of pan-genotypic direct-acting antiviral (DAA) therapy in cardiac transplantation prevents the transmission of hepatitis C virus (HCV) infection from an HCV-positive donor heart to an HCV-negative recipient patient..

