### ***Clinical hypotheses***

#### ***Hypothesis 1.***

We hypothesize that preemptive administration of pan-genotypic DAA therapy following cardiac transplantation will be well-tolerated and halt the development of HCV infection in a transplant recipient as evidenced by a negative HCV viral RNA at 12 weeks post treatment.

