Men must also agree that they will not donate sperm during the entire study period.

**Donor genotyping** – HCV genotyping will be performed by the MGH Core Lab. Because the treatment in this study is pan-genotypic, we do not need genotype results to return prior to medication administration; delays in HCV genotyping will not influence initiation of the study drug.

**Achievement of Sustained Virologic Response (SVR).** Patients who received an **HCV NAT-positive** donor heart who have an undetectable viral load 12 weeks after completing therapy (SVR 12) are patients in whom the use of DAA has successfully prevented HCV infection transmission. If during monitoring for these patients a positive viral load is detected and at the end of their 8 week therapy course, a plan will be made to extend the patient's course of Epclusa™ or Mavyret™ from 8 weeks to 12 weeks. We may also add additional Hep C medications to increase the chance of curing the Hep C infection. If this happens, we will plan to review all of these details in person with the patient and determine, based on recent updates and clinical practice, the best regimen with which to treat the patient and achieve HCV cure.

This study has received IND exemption from the FDA regarding use of pan-genotypic DAA therapy; a letter has been posted on the Attachments tab in Insight to provide documentation.

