## **VI. Biostatistical Analysis**

### Variables/Time Points of Interest

The primary variable of interest will be HCV RNA at the multiple time-points assessed during and after treatment.

The primary efficacy outcome “Prevention of HCV Transmission” will be determined by a negative HCV RNA test.

The safety outcomes include summation of treatment related adverse events and transplant rejection or patient mortality. On treatment eGFR, proteinuria, hemoglobin, and liver function tests will be summarized to assess safety.

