### Statistical Methods

Patient characteristics for this cohort (N=50 receiving HCV+ organ) will be presented with summary statistics for baseline demographics and clinical variables. The SVR12 rate will be presented and 95% CI constructed with the exact test. Mean and standard deviation for on-treatment laboratory values will be presented to analyze safety.

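### SVR12 is labelled as prevented transmission whatever the recipient's earlier HCV RNA; no per-patient never-viremic proportion is planned, and scoring of extended or added therapy is unstated

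*Combined protocol and SAP*

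**What the plan says.** Aim 1 in section II is to determine whether preemptive therapy "prevents the transmission of hepatitis C virus (HCV) infection from an HCV-positive donor heart to an HCV-negative recipient patient". Hypothesis 1 expects infection to be halted "as evidenced by a negative HCV viral RNA at 12 weeks post treatment".

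Section V, under Achievement of Sustained Virologic Response, turns this into a per-patient rule for recipients of NAT-positive hearts: "SVR 12) are patients in whom the use of DAA has successfully prevented HCV infection transmission". The sentences after it provide for a positive viral load, extension of the course from 8 to 12 weeks, and added HCV drugs.

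Section VI, Variables/Time Points of Interest, states: "The primary variable of interest will be HCV RNA at the multiple time-points assessed during and after treatment". The primary efficacy outcome, labelled as prevention of transmission, "will be determined by a negative HCV RNA test". No time point is attached to that test. Statistical Methods then states: "The SVR12 rate will be presented and 95% CI constructed with the exact test". The cohort is described as "N=50 receiving HCV+ organ", and the Background section explains that "throughout this protocol the use of HCV-positive refers to HCV nucleic acid testing (NAT)-positive organs".

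Aim 3 adds the proportion undetectable at each of nine study days: 7, 14, 28, 56, 84, 112, 140, 224 and 365.

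**The concern.** SVR12 shows that virus is absent 12 weeks after treatment. It does not show that virus never appeared. The protocol draws this line itself. The Background section hypothesises that therapy may either prevent infection or eliminate it, and treats sustained response as confirmation of cure. Section V speaks of cure when a viral load has been positive. A recipient of a NAT-negative organ who becomes viremic is treated reactively and followed to the same 12-week endpoint, where a negative result can only mean cure.

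Viremia before SVR12 is foreseeable under the plan. Section V allows study drug to start up to 7 days after transplant and makes provision for positive results. If some recipients are viremic and then clear, the rule in section V would still describe them as cases of prevented transmission. The data would support the weaker statement that infection was prevented or eliminated. Aim 1 asks about prevention, so the wording of the main conclusion is at stake.

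**Working it through.** The plan gives no target rate, power or interval width, so there is no design figure to reproduce. The check has four steps.

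**1. What the rule can distinguish.** For each recipient, let S mean undetectable RNA at the SVR12 sample, and let V mean detectable RNA at any scheduled post-transplant sample up to and including that one. Section V scores prevention as S alone. A recipient with a complete record and no V must have S, but S does not imply no V. If all n recipients reach S, the never-viremic count can lie anywhere from 0 to n.

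**2. Illustration at N = 50.** This N comes from Statistical Methods and is an upper limit. The viremic and extended counts are assumed, because the documents give none. Exact (Clopper-Pearson) limits for x of n are: lower = Beta quantile 0.025 with parameters (x, n−x+1); upper = Beta quantile 0.975 with parameters (x+1, n−x). For x = n = 50 the lower limit is 0.025^(1/50) = 0.929.

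| Quantity | x/50 | % | Exact 95% CI |
|---|---|---|---|
| SVR12, all clear | 50 | 100 | 92.9 to 100 |
| Never viremic, if 5 were viremic | 45 | 90 | 78.2 to 96.7 |
| Never viremic, if 25 were viremic | 25 | 50 | 35.5 to 64.5 |
| SVR12 if 3 extended-then-cured recipients count as not achieved | 47 | 94 | 83.5 to 98.7 |

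Rows 2 and 3 are both compatible with row 1. If the 3 extended recipients in row 4 count as achieved, the result returns to row 1.

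**3. Whether Aim 3 fills the gap.** Assume every recipient is sampled at every visit, and let p_j be the proportion undetectable at listed day j. The proportion undetectable on all k listed days lies between max(0, 1 − Σ(1 − p_j)) and the smallest p_j. With 96% at each of the nine days, the range is 1 − 9 × 0.04 = 64% up to 96%. Using only the seven listed days through Day 140, it is 1 − 7 × 0.04 = 72% up to 96%. The lower ends require the positives at each visit to be different patients. If viremia is early and then clears, the true value is close to the upper end.

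Section V itemises ten RNA samples after Day 0 through Day 140: Days 3, 7, 14, 28, 42, 56, 70, 84, 112 and 140. Aim 3 omits Days 3, 42 and 70, so viremia seen only on those days would not appear in it. Aim 3 therefore gives an upper bound on the never-viremic proportion, but not the proportion itself.

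**4. Which sample is the SVR12 sample.** The visit list fixes it at Day 140. The 12-week date is the last dose plus 84 days.

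| Course | Last dose | 12 weeks later | Time off drug at Day 140 |
|---|---|---|---|
| Ends 8 weeks after transplant | Day 56 | Day 140 | 12 weeks |
| Eight full weeks from a Day 7 start | Day 63 | Day 147 | 11 weeks |
| Twelve weeks from Day 0 or Day 7 | Day 84 or 91 | Day 168 or 175 | 8 or 7 weeks |

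The text is unclear on which of the first two rows applies. Section V describes the 8 weeks as post-transplantation and labels Day 63 as one week after the end of therapy, which implies Day 56. It also allows a start up to 7 days after transplant, and then describes dosing through course completion. The Study Drug Exposure text in section VII allows a first dose just before the operating room.

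**The case against.** SVR12 is the protocol's openly stated working definition, and no section defines transmission as any detectable RNA. Very early RNA might not represent established infection, so counting every sample is also an assumption. Serial RNA is collected and named as the primary variable, so a never-viremic count could be produced at any time. All of this is fair. It limits the size of the point, but a stated definition can still fail to answer the stated aim. In an open-label study, a rule fixed beforehand is also worth more than one chosen after the results are known.

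Three stronger readings are tempting, and the documents do not support them.

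- *The plan would conceal viremia behind a 100% prevention figure.* That headline has to be assembled from the rule in section V, the outcome label in section VI and the statistic in Statistical Methods, which promises only an SVR12 rate. Aim 3 would also expose widespread early viremia: if all 50 recipients were positive on Day 7, the Day 7 figure would be 0%.
- *Recipients rescued with longer or added therapy are counted as prevented.* Section V refers to completion of therapy without limiting it to 8 weeks, which would admit them. The cure wording, section VII's description of infection arising despite therapy, and the fixed Day 140 visit lean the other way. The scoring is unstated rather than wrong.
- *A wrong decision would follow.* Power/Sample Size calls this a pilot and sets no efficacy threshold.

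**Conclusion.** The point holds as a labelling and scoring defect that should be fixed. Section V attaches the word prevented to an endpoint that cannot separate prevention from cure, and no section plans the per-patient figure that could. Scoring of extended or added therapy is also left open.

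The size is unknown. The documents give no expected rate of viremia or extension, so the counts above show how far the figures can diverge, not how far they will. If no recipient is ever viremic and none needs extended or added therapy, the two proportions coincide apart from incomplete records. The harm is a mislabelled conclusion on Aim 1.

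**What to change.** These changes concern analysis, wording and sample timing only, and leave treatment as it is.

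1. In section V and in the outcome label in section VI, describe SVR12 as *prevented or eliminated HCV infection*. Align Aim 1 and Hypothesis 1 with that wording.
2. In Statistical Methods, alongside the SVR12 rate, report the per-patient proportion of the same recipients with no detectable HCV RNA at any scheduled post-transplant sample through the SVR12 sample, with an exact 95% CI. Reserve the word prevented for this figure. Show any version that leaves out early samples as a labelled sensitivity analysis.
3. Report SVR12 after the planned 8-week course, with extended or added HCV therapy counted as not achieved. Report SVR12 after any therapy separately.
4. Tie the SVR12 sample to 12 weeks after the actual last dose, with a stated visit window. Neither the fixed Day 140 nor the next itemised visit serves this purpose: for a recipient who finishes on Day 63, the next itemised RNA at least 12 weeks later is Day 224, and 224 − 63 = 161 days, or 23 weeks off drug. Reconcile the passages in sections V and VII on when study drug starts and ends, because the SVR12 date depends on them.

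The cost is low: revised wording, one extra count from RNA already scheduled, and a window rule. The prevented figure may come out lower than the SVR12 figure, and some SVR12 samples may fall off the fixed visit calendar.

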## **VI. Biostatistical Analysis**

### Variables/Time Points of Interest

The primary variable of interest will be HCV RNA at the multiple time-points assessed during and after treatment.

The primary efficacy outcome “Prevention of HCV Transmission” will be determined by a negative HCV RNA test.

The safety outcomes include summation of treatment related adverse events and transplant rejection or patient mortality. On treatment eGFR, proteinuria, hemoglobin, and liver function tests will be summarized to assess safety.

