### **Risks related to transplantation with an HCV infected heart (or heart and kidney)**

#### Liver problems

While unlikely, it is possible that DAAs will not result in the same efficacy following cardiac transplant. If HCV is transmitted and not eradicated it is possible that HCV infection post-transplant could cause health problems, including liver injury. In the short term, infection with HCV can cause a flu-like illness that includes fatigue, nausea, fever, abdominal pain, vomiting, joint pain, and yellowing of the skin (jaundice). Although it is very rare, infection with HCV can cause severe inflammation of the liver or even liver failure, including a condition called fibrosing cholestatic hepatitis. The risk of this complication in patients without HCV who receive a transplant from a donor with HCV is unknown. This complication can be treated and cured in the majority of cases with the HCV medications.

Cirrhosis of the liver can cause someone to experience leg swelling, yellow skin, skin itching, abdominal bleeding, shortness of breath, and the abdomen to fill with fluid (ascites). Liver failure can also cause death. Based on the limited data available, it would be extremely rare for someone in the study to experience liver failure in the first few months after transplantation because the study will be giving HCV treatment right away.

In the unlikely event that the patient develops HCV infection despite DAA therapy, we will be prepared to offer 2nd line treatment using + ribavirin or MavyretTM + ribavirin plus an additional DAA agent. In the unlikely event that this fails, there may be continued inflammation and scarring of the liver that over many years (10-30) that can lead to cirrhosis. If HCV causes cirrhosis, the patient is at increased risk of developing liver cancer, liver failure requiring a subsequent liver transplant, or death. Of note, we anticipate that with study drug treatment, or if necessary additional HCV therapies, we will be able to successfully prevent transmission and eradicate HCV in our study population.

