#### Additional risks of HCV:

HCV can cause other types of inflammation in the body, such as arthritis, rash, anemia, nerve pain and inflammation damage to your kidney transplant. These problems are rare, and affect less than 2% of people who have HCV. These problems should respond to effective HCV treatment.

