## **Risks Related to Study Procedures**

Risks of Blood Draws

The patient may have a bruise (a black-and-blue mark) or pain where researchers take the blood samples. There is also a small risk of feeling lightheaded, fainting, or infection. A total of up to 53 tablespoons of blood will be drawn over the course of the entire study.

Risks to an Embryo or Fetus, or to a Breastfeeding Infant

Because the effect, if any, of EpclusaTM or MavyretTM on an embryo or fetus is not known, the patient may not participate in this study if they are pregnant, breastfeeding, or planning to become pregnant. This is not a new requirement necessitated by this protocol, as patients on the cardiac transplant list must also agree to not become pregnant while awaiting and for a period of time after transplantation.

Study Drug Exposure

Patients will not receive the study drug until post-transplant or just prior to their transport to the operating room (OR) to receive a donor organ. We anticipate that the likelihood of a patient not receiving an organ after taking a dose of study drug is extremely low. However, in the event that a patient does receive the initial dose of study drug and not an HCV-positive heart, we would then plan to immediately stop the study drug. No additional study drug would be given unless the patient was again offered an HCV-positive organ and returning to the OR.

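### The adverse-event summary is limited to undefined treatment-related events and no safety population is named, so non-fatal harms of donor-derived HCV could go uncounted

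*Combined protocol and SAP*

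**What the plan says.** The safety outcomes are defined in Section VI, Variables/Time Points of Interest: "The safety outcomes include summation of treatment related adverse events and transplant rejection or patient mortality". The next sentence adds laboratory measures: "On treatment eGFR, proteinuria, hemoglobin, and liver function tests will be summarized to assess safety". Statistical Methods gives the analysis: "Mean and standard deviation for on-treatment laboratory values will be presented to analyze safety". Section VI has no summary of all adverse events or all serious adverse events. It does not define treatment-related or say who judges it.

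Collection is wider. Section V has emergent adverse events assessed at scheduled visits and unscheduled contacts, through a 365-day safety follow-up, with no condition on relatedness.

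Section VII names harms of the virus itself. Under Liver problems: "infection with HCV can cause severe inflammation of the liver or even liver failure, including a condition called fibrosing cholestatic hepatitis". A separate paragraph there covers effects outside the liver: "HCV can cause other types of inflammation in the body, such as arthritis, rash, anemia, nerve pain and inflammation damage to your kidney transplant".

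The only cohort named in Section VI appears in this sentence: "Patient characteristics for this cohort (N=50 receiving HCV+ organ) will be presented with summary statistics". Section I explains that "throughout this protocol the use of HCV-positive refers to HCV nucleic acid testing (NAT)-positive organs". Aim 2 in Section II concerns the safety and tolerability of DAA therapy in heart transplant recipients and sets no limit by donor status.

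**The concern.** What is new for these recipients is the infected organ as well as the drug. If the event count holds only events attributed to the drug, a non-fatal event caused by the virus can be recorded at a visit and still not appear in the safety result. Relatedness is an unblinded judgement here: the study is open-label with no comparator, and patients have just had major surgery and are on immunosuppressants. A filter that depends on that judgement is a weak base for Aim 2.

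The second part is the denominator. Some patients can receive a DAA without receiving a NAT-positive heart. If they are left out, Aim 2 is answered on fewer patients than were exposed. A reader should be able to tell from the plan who is counted.

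**Working it through.** The plan states no safety rate, expected event count or safety precision, so there is no figure to reproduce. The check is mainly a comparison of sections.

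1. **What treatment means.** Section III speaks of transplant and of treatment with study drug as two things. Section V uses treatment for DAA therapy. In Section VI, the sentence after the quoted one uses on treatment for the dosing period. The natural reading of treatment-related is therefore DAA-related. The documents do not settle this.

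2. **Whether HCV-derived harms reach the event count.** Section VII attributes severe hepatitis, liver failure, fibrosing cholestatic hepatitis, arthritis, rash, anemia, nerve pain and kidney-graft inflammation to HCV. On the natural reading, such an event enters the safety outcomes as an event only if it is judged related to the DAA or ends in rejection or death.

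3. **Whether the laboratory summaries fill the gap.** Liver tests, hemoglobin, eGFR and proteinuria correspond to several of these harms, so they fill part of it. Two limits remain.
   - *Time.* For an 8-week course, Section V lists liver tests, a metabolic panel and blood counts at six visits after treatment (Days 70, 84, 112, 140, 224 and 365). Section VI plans no safety summary of them. Infection that emerges after the course ends falls in this window.
   - *Form.* With 50 patients, a rise of size D in one patient moves the mean by D/50, or 2% of that rise. The SD would widen, but neither statistic says how many patients had a marked abnormality.

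4. **Late collection.** The Section V visit lists include adverse event reporting up to Day 112 but omit it at Days 140, 224 and 365. The same section describes a 365-day safety follow-up, and Section IX refers to assessment at each treatment visit. These do not agree.

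5. **Who is in the safety set.** Two DAA-exposed groups lie outside the N=50 label. Under Section V, recipients of NAT-negative hearts who develop a positive viral load start a DAA. Section VII, Study Drug Exposure, provides for the case where, "in the event that a patient does receive the initial dose of study drug and not an HCV-positive heart", dosing stops. Section VI neither includes nor excludes either group. The documents give no expected number for either, so the size of the omission cannot be calculated.

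6. **A bound from the one rate in the documents.** Section VII puts the extrahepatic problems at less than 2% of people who have HCV. If all 50 recipients were infected, the chance of at least one such event would be at most 1 − 0.98^50 = 0.636, with an expected count of at most 50 × 0.02 = 1. If only 5% to 20% of recipients had established infection (an assumption, not in the documents), the per-patient ceiling is 0.001 to 0.004. The chance is then 1 − 0.999^50 = 4.9% to 1 − 0.996^50 = 18.2%. For fibrosing cholestatic hepatitis in this setting, Section VII says the risk is unknown.

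**The case against.** The strongest reply is that HCV harm is well covered elsewhere. Rejection and death count with no relatedness condition. The laboratory measures track liver, blood and kidney. HCV RNA is the primary variable, SVR12 gets an exact 95% interval, and Aim 3 reports undetectable RNA at nine time points to Day 365, so persistent viremia could hardly go unreported. The word *include* does not close the list of safety outcomes, and treatment could be read as the whole strategy of organ plus DAA. Section IX also provides a three-monthly safety review.

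Much of this stands. A reader might infer that safety rests on treatment-related events alone. It does not, because the same paragraph names rejection, death and laboratory values. But RNA status shows infection, not clinical harm, and the laboratory summaries have the limits in steps 3 and 4. An open list leaves the remaining events to later choice, and the broader meaning of treatment, if intended, has to be written down.

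A reader might also infer that DAA-exposed patients without a NAT-positive heart are excluded from safety. The documents do not say so: the N=50 label is attached to patient characteristics, and Aim 2 is worded more broadly. Inclusion is unspecified. Section VII also expects dosing without receipt of an organ to be very unlikely.

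**Conclusion.** The point holds as a gap in definition. The adverse-event summary is restricted by an undefined term that most naturally means DAA-related, while collection is not so restricted. The other safety outcomes cover part of the difference, but not non-fatal HCV-derived events as events, least of all after the 8-week course. The safety population is not named.

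The size cannot be established from the documents. It is tempting to assume an HCV-derived event rate across all 50 recipients and conclude that a missed event is more likely than not. That is not supported: the rate below 2% applies to people who have HCV and to extrahepatic problems only, and 64% is reached only if every recipient is infected, which the therapy is meant to prevent. Nor does the plan specify a confidence interval for safety; its only interval is for SVR12. The conclusion rests on the natural reading of treatment-related and on the absence of any all-event summary in Section VI, not on these figures. It is an inexpensive improvement that should be made before the data are analysed.

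**What to change.** In Section VI, Variables/Time Points of Interest:

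- Summarise all adverse events and all serious adverse events from first DAA dose or transplant, whichever is earlier, through last follow-up, regardless of attribution. Show DAA-related and donor-HCV-related events as sub-lines, and state who judges each.
- List the HCV-derived harms named in Section VII as a category of their own.
- Report safety for everyone given at least one DAA dose (pre-emptive, reactive, or dosed without receiving an HCV-positive heart), alongside the NAT-positive-heart cohort.
- Extend the liver test, hemoglobin and eGFR summaries to the post-treatment visits. Add counts of patients with marked abnormalities, by thresholds set in advance, to the mean and SD.

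In Section V, reconcile the Day 140, 224 and 365 visit lists with the 365-day safety follow-up, and align Section IX.

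The cost is wording, extra table rows and adverse event entries at the late visits; the bloods are already scheduled. The downside is larger raw event counts, many from transplantation itself, which the sub-lines help the reader to separate.
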